## Individual pharmacodynamic response to the nitroglycerin challenge

An exploratory analysis was planned to identify the incidence of a patient specific pharmacodynamic response to the nitroglycerin challenge. A PD response threshold was set as a post-administration PVD > 1.8 standard deviations from the baseline, which was calculated by averaging the intra-patient variance between the three baseline PVD video sequences, which was then pooled across the entire cohort. This 1.8SD threshold was set to achieve 90 percent confidence interval (assuming a one-sided alpha, since there was only an anticipated increase in PVD). This method has been used in previous Phase 0 trials to provide a statistically rigorous threshold for individualized PD responses to novel therapeutic interventions.

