### Study design and drug administration

This investigator-initiated, open-label study was conducted at the Hospital of the University of Pennsylvania, an urban quaternary academic medical center. The study was approved by the University of Pennsylvania's institutional review board, registered with ClinicalTrials.gov (NCT05102734), and conducted in accordance with the principles of the Declaration of Helsinki. Sample size was determined based on an anticipated 30% increase in TVD, and setting a one-sided α of 0.1, and ß of 0.8. A 1% topical nitroglycerin solution was prepared immediately prior to enrollment by reconstituting 400 mcg of nitroglycerin (Pfizer Pharmaceuticals, New York, NY, USA) in 4mL of sterile water within a dropper bottle that would administer the solution in 0.05mL aliquots. Two drops (0.1 mL) of the 1% nitroglycerin solution (5 mcg or 2.27\*10^-2 μmol per drop)

were applied to the sublingual space after obtaining baseline post-operative microcirculation images. A microdosing (approximately 1/50th of the lowest therapeutic sublingual dose) was administered to avoid any systemic effects.

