### Microcirculatory imaging and analysis

Sublingual microcirculation imaging was performed using HVM (CytoCam, Braedius Medical BV, the Netherlands) in the preoperative staging area (for controls) or within 2 hours of arriving to the intensive care unit after surgery by a trained member of the investigative team ([name] or [name]). The sublingual microcirculation was measured at 3 time points: baseline, 3 minutes post-nitroglycerin, and then 30 minutes later. Images were obtained by gently placing the videomicroscope under the subject's tongue until an adequate view of the microcirculation was obtained. A series of six second video clips (120 frames) duration were taken at each time point with attention to quality factors, especially the absence of pressure artifact, excess saliva, and proper location in accordance with the accepted consensus for microcirculation analysis. Image quality was assessed using the 6-factor Massey quality score, which scores each video for appropriate illumination, duration, focus, content, stability, and pressure. Images were only included in the final analysis if the Massey quality score was < 10 . Acceptable clips were deidentified and coded for analysis after enrollment was complete.

Microcirculation videos were exported using commercial software (CCTools 2, Braedius Medical BV, the Netherlands) and manually analyzed using the validated Automated Vascular Analysis software (AVA 3.2; Microvision Medical B.V., the Netherlands). Video analysis was performed by trained investigators ([name] and [name]) who were blinded to the conditions of the subject. Only microvessels <  $20 \, \infty m$  in diameter were included in the calculation of TVD and PVD.

Red blood cell flow velocity was calculated within appropriate venules 20-30 ∞m in diameter by manually measuring the slope of individual RBC movement within software generated space-time diagrams . Microcirculatory function was quantified according to the current best practice guidelines for microcirculation imaging. Blood flow within each microvessel was graded using a semiquantitative scale, based on the vascular flow pattern ranging from 0-3 (0=no flow, 1=intermittent, 2=sluggish, or 3=continuous flow). Vessel perfusion was dichotomized as nonperfused (no flow or intermittent flow) or perfused (continuous or sluggish) for the calculation of PPV and PVD.

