### **Statistical Analysis**

Data normality was assessed using the D'Agostino-Pearson omnibus normality test. Global hemodynamic and microcirculation variables are reported as mean  $\pm$  SD. Variables that were not normally distributed are reported as median with interquartile range [ $25^{th} - 75^{th}$  percentiles]. Student t-test was used to test for differences between normally distributed variables. Mann-Whitney U test was used to analyze non-normal data. Repeated measure one-way ANOVA with Tukey's post-hoc testing was used to assess for changes in microcirculatory function during the nitroglycerin challenge. Inter-rater reliability between coders was assessed in 10% of the videos using a Bland-Altman plot. Statistical analysis was conducted using Prism v 8.0 (Graph-Pad Software, San Diego, CA). Statistical significance was assumed at p < 0.05.

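### The response incidence is a count above a cut-off that, on the plan's own 90%, about 1 in 10 non-responders cross, with no interval and no comparison with that rate

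*Combined protocol and SAP*

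**What the plan says.** The section on individual pharmacodynamic response gives the aim: "An exploratory analysis was planned to identify the incidence of a patient specific pharmacodynamic response to the nitroglycerin challenge". The rule is: "A PD response threshold was set as a post-administration PVD > 1.8 standard deviations from the baseline". The SD was "calculated by averaging the intra-patient variance between the three baseline PVD video sequences, which was then pooled across the entire cohort". The confidence level is one-sided: "This 1.8SD threshold was set to achieve 90 percent confidence interval". The section then cites an earlier phase 0 method as the source of the threshold and stops there.

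Three other places bear on the point:

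- Microcirculatory imaging and analysis: the microcirculation was "measured at 3 time points: baseline, 3 minutes post-nitroglycerin, and then 30 minutes later". There are therefore two post-dose values per patient, and the rule does not say which one counts.
- Study design and drug administration: "Sample size was determined based on an anticipated 30% increase in TVD, and setting a one-sided α of 0.1, and ß of 0.8". This concerns a different variable, total vessel density (TVD), and gives neither an SD nor a number of patients.
- Statistical Analysis: "Repeated measure one-way ANOVA with Tukey's post-hoc testing was used to assess for changes in microcirculatory function during the nitroglycerin challenge". The other methods listed are the t-test, the Mann-Whitney test and a Bland-Altman plot for rater agreement. None of them applies to a proportion of responders.

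**The concern.** A one-sided 90% cut-off for each patient accepts a 10% chance of labelling that patient a responder when nothing has happened. If no patient responds, the expected count above the cut-off is one tenth of the cohort, not zero. The plan treats the share above the cut-off as the incidence of response. It sets no reference rate, no minimum count, no interval and no test.

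In a small cohort, two or three labelled patients could therefore be reported as people in whom the challenge worked, although clip-to-clip noise alone could produce that number. Nothing in the planned output would let a reader tell the two situations apart.

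**Working it through.** **Inputs.** The 1.8 SD multiplier, the one-sided 90% and the use of three baseline clips come from the section on individual response. The two post-dose times come from the imaging section. The number of patients is not given, so n = 10, 15 and 20 are assumed. Patients are taken as independent, and clip noise as normal with known SD and as the only source of variation.

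**Step 1: reproduce the plan's figure.** The difference between two single readings with equal SD has an SD of √2 times the clip SD. The one-sided 90% cut-off is then 1.2816 × √2 = 1.81 clip SDs, which rounds to the stated 1.8. In reverse, 1 − Φ(1.8/√2) = 1 − Φ(1.273) = 10.2%. The stated 90% is therefore correct for one clip against one clip. A two-sided 90% would need 1.645 × √2 = 2.33, which does not match.

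**Step 2: what the crossing share estimates.** Let π be the true share of responders, s the chance that a true responder crosses and f the chance that a non-responder crosses. The expected crossing share is π·s + (1 − π)·f. With π = 0 it equals f, about 10%, rather than 0.

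**Step 3: counts with no effect in anyone.** With f = 0.10, the count follows a binomial(n, 0.10) distribution. The last column gives the smallest count whose upper-tail probability is at most 0.05.

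| n (assumed) | Expected count | P(≥1) | P(≥2) | P(≥3) | Count needed |
|---|---|---|---|---|---|
| 10 | 1.0 | 65% | 26% | 7.0% | 4 (p = 0.013) |
| 15 | 1.5 | 79% | 45% | 18% | 5 (p = 0.013) |
| 20 | 2.0 | 88% | 61% | 32% | 5 (p = 0.043) |

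Exact 95% intervals show what a bare count conceals. Two of 10 gives 2.5% to 56%, and three of 10 gives 6.7% to 65%. Both include 10%.

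**Step 4: how far the 10% depends on the reading of the rule.** The section does not say whether the PVD compared is one clip or a mean of clips. With the multiplier fixed at 1.8 clip SDs, the false-positive rate is 1 − Φ(1.8/√v), where v is the variance of the difference in units of the clip variance.

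| Comparison | v | False-positive rate |
|---|---|---|
| Single clip v single clip | 2 | 10.2% |
| Single clip v mean of three | 4/3 | 6.0% |
| Mean of three v mean of three | 2/3 | 1.4% |
| Single v single, either post-dose time qualifies | 2 at each time, correlation 0.5 from the shared baseline | about 17% |

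The rate matters for the count. At 1.4% and n = 10, noise gives at least one apparent responder in 13% of trials and at least two in 0.8%, so two of 10 would already exceed the null at 0.05. At 17% and n = 10, five of 10 would be needed (four of 10 has tail probability 0.074).

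**The case against.** **The analysis is exploratory.** The study was sized on a mean change, change during the challenge is tested at group level, and no decision rule depends on the responder count. This stands, and it limits the consequence. It does not make the crossing share an incidence, and an exploratory proportion still needs an interval and a reference rate to be readable.

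**The 10% is not settled.** Several clips were taken at each time point, so a comparison of means is at least as plausible as one clip against one clip. This also stands. If means of three are compared and clip noise is all there is, the false-positive share is small and a fixed 10% benchmark would be too strict. If either post-dose time counts, 10% would be too lenient. The comparison rate must therefore follow from the stated comparison and not be fixed at 10% by default. Drift between time points, which variation among baseline clips may not capture, would raise the rate.

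**The method is cited.** The citation is offered for the individual threshold. It does not put a cohort-level comparison into this plan.

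**Stronger readings.** A reader might infer that the cut-off misses most true responders, or that a low count could hide a response in everyone. The documents do not support this. They give no clip SD for PVD, the 30% used for sizing refers to TVD, and a response in every patient would be a mean shift, which the repeated-measures ANOVA examines. A reader might also infer that proper reporting must weaken the trial's claim. The documents contain no results, and a high count would be strengthened by the comparison: six of 10 against 10% has a tail probability of about 0.0001.

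**Conclusion.** The point holds. Followed as written, the plan reports as incidence a share that includes false positives, about 10% of non-responders on its own stated confidence level, and it provides neither an interval nor a null comparison. With no effect and 10% per patient, at least two apparent responders would be seen in 26% of trials at n = 10 and 61% at n = 20.

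These figures rest on assumed sample sizes, independence between patients and a comparison of one clip with one clip. Under other readings of the rule the per-patient rate is 6.0%, 1.4% or about 17%, so its size is uncertain until the rule is made specific. The absence of an interval and a comparison does not depend on which reading applies. Because the analysis is exploratory, this is a correction that should be made and not a threat to the group-level analysis.

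**What to change.** In the section on individual pharmacodynamic response:

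1. State which PVD value is compared before and after dosing (single clip or mean, and of how many clips) and which post-dose time counts.
2. State the false-positive rate that 1.8 SD gives for that comparison.
3. Report the number and proportion of patients above threshold, under that name, with an exact 95% interval.
4. Compare the count with the rate in item 2 by an exact one-sided binomial test, labelled exploratory. Describe the result as evidence of individual response only if the count exceeds that rate on the test.

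Add the interval and the test to the Statistical Analysis section.

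The cost is a few lines of text and a little more analysis of data already collected. The downside for the investigators is that a low responder count could no longer be presented as evidence of response.

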## Patient data and safety monitoring

Subject demographics, pre-operative risk score (euroSCORE II) and medical history were collected during initial screening. Cardiac index (CI), central venous pressure (CVP), pulmonary artery pressure (PAP), and mixed venous oxygen saturation (SvO2) were continuously monitored by pulmonary artery catheter (Edwards Lifesciences LLC, Irvine, CA, USA). Arterial blood pressure was measured continuously using a standard invasive arterial line. Systemic hemodynamic data, vasopressor infusion doses, and mixed venous oxygen saturation were

recorded at baseline then every 3 minutes for 30 minutes after application of the topical nitroglycerin solution. The vasopressor-inotrope score (VIS) was calculated to summarize the degree of post-operative vasoactive support was required at the time of the study. Norepinephrine equivalents were calculated for each patient at each time point.

### Availability of data and materials

The dataset supporting the results of this report is available via the Zenodo research data repository.

### **Statistical Analysis**

Data normality was assessed using the D'Agostino-Pearson omnibus normality test. Global hemodynamic and microcirculation variables are reported as mean  $\pm$  SD. Variables that were not normally distributed are reported as median with interquartile range [ $25^{th} - 75^{th}$  percentiles]. Student t-test was used to test for differences between normally distributed variables. Mann-Whitney U test was used to analyze non-normal data. Repeated measure one-way ANOVA with Tukey's post-hoc testing was used to assess for changes in microcirculatory function during the nitroglycerin challenge. Inter-rater reliability between coders was assessed in 10% of the videos using a Bland-Altman plot. Statistical analysis was conducted using Prism v 8.0 (Graph-Pad Software, San Diego, CA). Statistical significance was assumed at p < 0.05.

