# Study Protocol and Statistical Analysis Plan

### **Patient selection**

Adult patients (age>18 years) receiving elective cardiac surgery requiring cardiopulmonary bypass were screened for eligibility from August-October 2021. Written informed consent was obtained from eligible patients prior to surgery. Patients were excluded if they had a nitroglycerin allergy, were taking oral phosphodiesterase inhibitors, were unable to tolerate microcirculatory flow image acquisition or did not have a pulmonary artery catheter for continuous cardiac output monitoring after surgery. Patients only received the study drug if they met the clinical criteria for circulatory shock, defined as having postoperative vasopressor-dependent hypotension or low cardiac output requiring inotropic support, with signs of end-organ injury (capillary refill time > 3 seconds, lactate > 2, SvO2 < 60%). A second cohort of patients were enrolled to serve as a preoperative control, which were matched to the experimental group for age, co-morbidities, and planned operation. Study data were collected and recorded using a well-established clinical database tool (REDCap, Vanderbilt University, Nashville, TN) hosted at the University of Pennsylvania.

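### Minor, cheap improvement: the plan names the pooled-variance Student t-test with no provision for unequal variances; Welch's test is the safer default for an unpaired comparison of shock patients with controls

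*Combined protocol and SAP*

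**What the plan says.** The Statistical Analysis section gives three rules for testing.

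- Normal variables: "Student t-test was used to test for differences between normally distributed variables".
- Non-normal variables: "Mann-Whitney U test was used to analyze non-normal data".
- Change within patients: "Repeated measure one-way ANOVA with Tukey's post-hoc testing was used to assess for changes in microcirculatory function during the nitroglycerin challenge".

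The level is stated as "Statistical significance was assumed at p < 0.05", without saying whether tests are one- or two-sided. Normality is checked. No check of variances and no unequal-variance method is mentioned. The t-test sentence does not say which groups are compared or whether the test is paired.

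Under Patient selection, "A second cohort of patients were enrolled to serve as a preoperative control", and these controls were "matched to the experimental group for age, co-morbidities, and planned operation". The section gives neither their number nor the matching ratio, and does not say whether matching was patient by patient or at group level.

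**The concern.** Student's test estimates one common variance from both groups. Here one group is selected for circulatory shock after surgery, and the other is imaged before elective surgery. Nothing in the documents supports equal spread between two such groups.

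Equal numbers are not assured either. Patients consented before surgery but received the study drug only if they later met the shock criteria, so the size of the shock group was not fixed at consent. Clips that fail the image-quality criterion are also dropped, which could unbalance the groups further.

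If sizes and spreads both differ, the pooled standard error is biased. It is too small when the smaller group is the more variable one, and too large when the larger group is. The p values and confidence intervals for the group comparison would be off accordingly, and the documents do not let a reader tell in which direction.

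**Working it through.** **1. Which comparison the t-test serves.** Within-patient change has its own method, the repeated-measures ANOVA. The counterpart named for non-normal data, Mann-Whitney U, is an unpaired test. The controls are the only second group. The natural reading is therefore an unpaired comparison of shock patients with controls. This is an inference, not the plan's wording.

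**2. Inputs.** From the documents: significance at 0.05. Not in the documents, and so assumed: two-sided testing, group sizes of 5 to 20, normal data, and a shock SD twice the control SD (2 against 1) as the main scenario. The plan states no figure on this point, so there is nothing to reproduce.

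**3. Why the direction depends on which group is larger.** The true variance of the difference in means is s₁²/n₁ + s₂²/n₂. Student's test in effect uses

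[((n₁−1)s₁² + (n₂−1)s₂²)/(n₁+n₂−2)] × (1/n₁ + 1/n₂).

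Group 1 is shock, with s₁ = 2 and s₂ = 1:

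- 10 v 20: true 4/10 + 1/20 = 0.450; pooled (9×4 + 19×1)/28 × 0.15 = 0.295. The standard error is √(0.295/0.450) = 0.81 of what it should be.
- 20 v 10: true 4/20 + 1/10 = 0.300; pooled (19×4 + 9×1)/28 × 0.15 = 0.455. The ratio is √(0.455/0.300) = 1.23.
- 10 v 10: true 4/10 + 1/10 = 0.500; pooled (9×4 + 9×1)/18 × 0.2 = 0.500. The two agree, and only the degrees of freedom differ.

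**4. Type I error at nominal 0.05.** Simulation with equal means, 200,000 data sets per scenario, SD ratio 2:

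| Shock v control | Student | Welch |
|---|---|---|
| 10 v 20 | about 0.11 | 0.052 |
| 20 v 10 | 0.019 | 0.049 |
| 10 v 15 | 0.087 | 0.051 |
| 15 v 10 | 0.030 | 0.048 |
| 5 v 15 | 0.157 | 0.056 |
| 15 v 5 | 0.010 | 0.049 |
| 5 v 5 | 0.059 | 0.049 |
| 10 v 10 | 0.055 | 0.051 |
| 20 v 20 | 0.052 | 0.050 |

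With a milder SD ratio of 1.5, Student gives 0.085 at 10 v 20 and 0.028 at 20 v 10. Over all sizes tried and SD ratios from 1 to 3, Welch stayed between 0.044 and 0.057.

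**5. What Welch costs if the SDs are equal.** Power, with the difference chosen so that Student has about 80%:

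| Sizes | Student | Welch | Loss (points) |
|---|---|---|---|
| 10 v 10 | 80.1% | 79.6% | about 0.5 |
| 5 v 5 | 79.1% | 76.7% | about 2 |
| 10 v 20 | 80.0% | 78.2% | about 2 |
| 5 v 15 | 81.1% | 72.3% | about 9 |

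**6. If controls were matched one to one.** With 10 pairs, a within-pair correlation of 0.5 and a true difference of 1 SD, unpaired Welch has a type I error of 0.009 and power of 58%. The paired t-test has 0.050 and 80%. In that case the paired test is the better replacement. With no within-pair correlation the order reverses slightly (56% for Welch, 51% paired).

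**The case against.** The strongest reply is that no defect has been shown. Harm needs unequal sizes and unequal spreads together, and the documents report neither. The one design fact about the controls is that they were matched; if that was one to one, sizes are equal and Student's error is 0.052 to 0.059 at an SD ratio of 2. It is also assumed that the shock group varies more, since selection on shock criteria could narrow some variables. And Welch does nothing for individually matched data.

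Much of this stands and limits the point. A reader might infer that the reported p values are wrong; the documents do not support that, because without sizes and SDs neither an error nor its direction can be shown. A reader might also take the plan to prescribe a pooled test for shock v control explicitly; it does not, and the link is inferred. Nor is Welch free, as the power losses show, and they are largest in small, unbalanced groups.

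What survives is that the named test relies on an assumption that the plan neither checks nor justifies for these two groups. No matching ratio is given to make equal sizes safe, and an alternative exists that holds its error rate near 0.05 in every scenario tried.

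**Conclusion.** The point holds as a minor improvement. Under an assumed SD ratio of 2, Student's type I error could be about twice nominal (0.11 at 10 v 20) or less than half of it (0.02 at 20 v 10), while Welch stays near 0.05. At equal sizes the difference is trivial. These figures rest on assumed group sizes, SDs and two-sided testing, and on reading the t-test sentence as an unpaired comparison of shock patients with controls.

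It would be tempting to extend the doubt to the main result. That is not supported: change during the nitroglycerin challenge is tested by repeated-measures ANOVA, which this point does not touch.

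**What to change.** In the Statistical Analysis section, say that the t-test compares shock patients with preoperative controls, give both group sizes, and say whether controls were matched individually. Then:

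- for unpaired comparisons, replace the Student t-test with Welch's unequal-variance t-test, and report the difference in means with its 95% confidence interval;
- if controls were matched individually in pairs, use a paired t-test instead.

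The cost is a few words and an option in the analysis software. The statistical price is the loss of power tabulated above if the SDs are in fact equal: small at balanced or moderately unbalanced sizes, about 9 points at 5 v 15. The document is written in the past tense and cites a deposited dataset, so rerunning these comparisons should need no new data.

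### The omnibus F test and the baseline-to-30-minute comparison cannot separate a nitroglycerin effect from drift over time; the drug conclusion should rest on one 3-minute contrast

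*Combined protocol and SAP*

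**What the plan says.** The Microcirculatory imaging and analysis section sets the schedule: "The sublingual microcirculation was measured at 3 time points: baseline, 3 minutes post-nitroglycerin, and then 30 minutes later". For treated patients, imaging takes place "within 2 hours of arriving to the intensive care unit after surgery". Under Study design and drug administration, the drops always follow the baseline images, and the study is open-label; no vehicle or sham drop is described.

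The only comparison group appears under Patient selection: "A second cohort of patients were enrolled to serve as a preoperative control". It is imaged before surgery.

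The Statistical Analysis section then says: "Repeated measure one-way ANOVA with Tukey's post-hoc testing was used to assess for changes in microcirculatory function during the nitroglycerin challenge". Significance is taken at p < 0.05. No contrast among the three times is given priority, and no adjustment for time or for changes in vasoactive support is specified, although haemodynamics and vasopressor doses are "recorded at baseline then every 3 minutes for 30 minutes after application of the topical nitroglycerin solution".

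**The concern.** The challenge is meant to show whether nitroglycerin changes the microcirculation. The null hypothesis of a one-way repeated-measures ANOVA on time is that the three time means are equal. The order is fixed and nobody is imaged over the same postoperative interval without the drug, so drug and elapsed time are confounded. The preoperative cohort cannot estimate a trend that arises after bypass. Blinded video reading guards against reader bias, not against a real change over time.

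The patients are in shock and early after surgery, so some spontaneous movement over half an hour is plausible, although the documents do not describe any. The comparisons are not equally exposed to it. Under a steady drift, baseline to 3 minutes picks up about one eleventh of the total, and baseline to the last image picks up all of it.

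What is at stake is the reading of a significant result. With no contrast named in advance, a significant F or 30-minute pair could be reported as a drug effect. A 30-minute value that stays high could likewise be taken as persistence of the drug when it reflects recovery.

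**Working it through.** The plan gives no sample size, SD, power result or drift figure, so there is no stated figure to reproduce. The check asks how often each test rejects when the drug does nothing and only drift is present.

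**Inputs from the documents.** Three times in fixed order: 0, 3 and, on a literal reading, 33 minutes (3 + 30). The test level is 0.05, and the method is repeated-measures ANOVA with Tukey pairs.

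**Assumptions.** n = 10 or 20. Linear drift totals d, in units of the within-patient SD at one time point (σ = 1). Errors are normal and independent within patient. The paired t-test is two-sided at 5%; the plan does not state sidedness for its significance level.

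**Means under drift alone.** 0, d × 3/33 = d/11, and d. Their average is 4d/11, so the deviations are −4d/11, −3d/11 and 7d/11. The sum of squares is (16 + 9 + 49)d²/121 = 74d²/121.

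**Omnibus F.** Degrees of freedom are 2 and 2(n−1), and the noncentrality is λ = n × 74d²/121. For n=10, d=1: λ = 6.12, critical value 3.555, rejection 52%. For n=20, d=1: λ = 12.23, critical value 3.245, rejection 86%.

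**Tukey pair.** Noncentral t on 2(n−1) df with noncentrality δ√(n/2), compared with the studentized-range critical value divided by √2. Here δ = d for baseline to 30 minutes and d/11 for baseline to 3 minutes.

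**Paired t-test, 3 minutes minus baseline.** Noncentral t on n−1 df with noncentrality (d/11)√(n/2).

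Rejection rates with no drug effect:

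| n | d | Omnibus F | Tukey 0–30 | Tukey 0–3 | Paired t 0–3 |
|---|---|---|---|---|---|
| 10 | 0 | 5.0% | 2.0% | 2.0% | 5.0% |
| 10 | 0.2 | 6.6% | 3.1% | 2.0% | 5.0% |
| 10 | 0.5 | 16% | 10% | 2.1% | 5.1% |
| 10 | 1.0 | 52% | 40% | 2.2% | 5.4% |
| 20 | 0 | 5.0% | 2.0% | 2.0% | 5.0% |
| 20 | 0.2 | 8.6% | 4.4% | 2.0% | 5.0% |
| 20 | 0.5 | 30% | 21% | 2.1% | 5.2% |
| 20 | 1.0 | 86% | 76% | 2.4% | 5.9% |

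A Tukey pair has a null level of about 2%, because the 5% is shared over three pairs.

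**Power for a transient effect.** Take a 1-SD effect at 3 minutes, gone by the last image, with no drift and n=10. The noncentrality is √(10/2) = 2.24. The paired t-test has power 0.51 and the Tukey pair 0.40.

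**Interpolated contrast.** This is the 3-minute value minus (10/11 × baseline + 1/11 × last value). Its variance is 1 + (10/11)² + (1/11)² = 1.835, against 2 for the simple difference. Under linear drift its expectation is zero, so it holds 5% exactly. The paired test is at most 5.9% in the table, so interpolation gains less than one percentage point.

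**Front-loaded drift.** Suppose drift totals 1 SD but follows 1 − exp(−t/τ), scaled to reach 1 at 33 minutes. With τ = 5 minutes the 3-minute mean is 0.45. The interpolated contrast then rejects 12% (n=10) and 21% (n=20), and the paired t-test 15% and 27%. With τ = 3 minutes the 3-minute mean is 0.63, and the rates are 21% and 40% against 24% and 48%. Neither contrast is protected against recovery that fast.

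**If the last image is at 30 minutes after the drug.** The 3-minute share becomes 3/30 = 1/10 and the interpolation weights 9/10 and 1/10. The conclusion does not change.

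**The case against.** The strongest reply is that the plan claims no more than the test delivers. It says the ANOVA assesses changes during the challenge, and nowhere says that the F test or the 30-minute pair will be cited as proof of a drug effect or of persistence. That is correct: such a misreading is a risk left open by the lack of a named contrast, not something the documents state.

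A reader might also infer that ordinary recovery after bypass does make these tests reject. The documents do not support that. They report no recovery, direction or rate, and no sample size or SD. At a drift of 0.2 SD the F test is only at 6.6% to 8.6%; the large figures need a drift of about half an SD or more.

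Nor does the concern undermine the whole challenge. The plan's own baseline-to-3-minute Tukey pair stays near 2% under every linear drift shown. A rise at 3 minutes that has gone by the last image would not fit monotone recovery.

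Finally, it is tempting to make the interpolated contrast the decisive test and call it drift-corrected. It barely improves on a plain paired test under linear drift and fails under front-loaded drift, so it does not deserve that role.

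What remains is that two of the tests the plan names cannot separate drug from time, and the plan does not say which comparison answers the drug question.

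**Conclusion.** The point holds in conditional form. Drug and time are confounded in the omnibus F and the baseline-to-30-minute pair, and either can reject without a drug effect if the microcirculation drifts. The inflation runs from slight (6.6% at n=10, drift 0.2 SD) to severe (86% at n=20, drift 1.0 SD) for the F test. Those sizes rest on assumed n, assumed linear drift, normal data and independent within-patient errors; none comes from the documents. The baseline-to-3-minute comparison is little affected by slow drift. It remains open to rapid recovery and to step effects from replacing the probe or from the drop itself, which no reanalysis of these data can remove.

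This is worth changing as an inexpensive improvement in what the analysis can claim. It does not show that any result is wrong.

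**What to change.** In the Statistical Analysis section:

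1. Name the within-patient change from baseline to 3 minutes, tested by a paired t-test with its sidedness stated, as the single contrast for each microcirculatory measure on which the conclusion about nitroglycerin rests.
2. Report the omnibus F and the baseline-to-30-minute pair as descriptions of change over time, not as evidence of a drug effect or of its persistence.
3. Optionally add the interpolated contrast as a sensitivity analysis, using recorded clip times if available. State that it removes only roughly linear drift, and not front-loaded recovery or a step effect from probe replacement or the drop.

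No new data are needed. For a transient 1-SD effect at n=10, power is 0.51 rather than the Tukey pair's 0.40, because one contrast per measure no longer pays for three; multiplicity across measures is not addressed by this change. The plan gives up a drug claim at 30 minutes. If the effect persists in full at the last image, the optional contrast loses 1/11 of it. The document is written in the past tense and its dataset is already deposited, so the change must be reported as made after data collection.
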